### 7.2.2 Plasma pharmacokinetic analysis

Listings with plasma concentrations of AL-335, ALS-022399 and ALS-022227, SMV and ODV (including PK blood sampling dates and times) and PK parameters will be provided by cohort, dose, and subject. These listings will be performed on all subjects with an available profile (complete or incomplete), including those who are excluded from the PKS.

A specific listing will be also done focussing on subjects who either discontinue the study for an adverse event, experience a severe adverse event or a serious adverse event.

Individual plasma concentrations for all subjects and PK parameters of AL-335, ALS-022399 and ALS-022227, SMV and ODV including descriptive statistics for subjects participating in the PK substudy will be presented in tables by cohort and by pooled cohorts.

Graphs for plasma concentration versus time profiles of AL-335, ALS-022399 and ALS-022227, SMV and ODV will be generated on linear and log/linear coordinates for arithmetic mean ( $\pm$ SD) by cohorts.

In addition, the plasma concentration versus time profiles of AL-335, ALS-022399 and ALS-022227 will also be presented on the same graph or as a separate graph on linear and log/linear coordinates for arithmetic mean ( $\pm$ SD) by pooled cohort.

Moreover, the plasma concentration versus time profiles of AL-335, ALS-022399 and ALS-022227, SMV and ACH-3102 will be presented graphically on linear and log/linear coordinates for each subject.

Pre-dose (“trough”) concentrations of AL-335, ALS-022399 and ALS-022227, SMV and ODV for all subjects at all available timepoints will be presented graphically on linear coordinates for arithmetic mean ( $\pm$ SD) by cohorts and by pooled cohorts.

Scatter plots will be generated for the comparison of  $C_{\text{trough}}$ ,  $C_{\text{max}}$ , and  $AUC_{0-\tau}$  parameters of AL-335, ALS-022399, ALS-022227, SMV and ODV by cohorts and by pooled cohorts.

## 8. Safety data

The safety analyses will be performed on the safety set.

### 8.1 Adverse events

Adverse events, including pre-treatment events, will be recorded from the time of consent through the completion visits, for the treatment and follow-up phase combined.

Adverse events will be coded according to MedDRA® Version 19.1.

A treatment-emergent adverse event (TEAE) is an adverse event that occurs after the first IMP administration or that was present prior to dosing but exacerbated after the first IMP administration.

Adverse events will be summarised in tables as follows (overall and by System Organ Class (SOC) and Preferred Term (PT)):

- Number and percentage of subjects with at least one adverse event and number of adverse events for each cohort,
- Number and percentage of subjects with at least one TEAE and number of TEAEs for each cohort,
- By intensity, with the number and percentage of subjects with at least one TEAE and number of TEAEs for each cohort,
- By causality of each treatment, with the number and percentage of subjects with at least one TEAE and number of TEAEs for each cohort.

Moreover, an overall summary table of all TEAEs will be presented.

In addition, summary tables will also be presented for TEAEs, serious TEAEs, TEAEs leading to any study drug discontinuation, severe or life threatening (i.e. Grade 3 / 4) TEAEs, and TEAEs with fatal outcome by decreasing frequency of PT.

The incidence and comparable prevalence rate per 2-week time interval for any AEs will be summarized and plotted by cohort.

Note: Repetitions will only be counted once in summary tables. Repetitions are defined as follows: if a given subject presents several adverse events with the same preferred term during the same phase (treatment and follow-up phase combined), only one event is counted, the others are considered repetitions or recurring episodes. The start time of the event will be the start time of the first occurrence, the end time will be the end time of the last episode. The intensity will be the highest recorded intensity for all episodes. The causality will be the highest likelihood recorded for all episodes.

A summary table of TEAEs of special interest (cardiac events, increased bilirubin (hyperbilirubinemia, blood bilirubin increased), rash and photosensitivity) will be also presented (see Appendix 4 for detailed list of SMQs).

The incidence rates for each event of interest by WHO toxicity grades and relationship to study drugs will be summarized. Time to the first occurrence of the events of interest will be summarized and Kaplan-Meier curves will be plotted.

The incidence and comparable prevalence rate per 2-week time interval for AEs of special interest will be summarized and plotted by cohort.

Bar graphs of the worst toxicity grade of cardiac events over time by cohort will be plotted.

All adverse events for subjects who met the Study Stopping Rules (i.e. <1 log decline in HCV RNA after 4 weeks of treatment) will be listed.

All TEAEs reported in the CRF will be listed with the SOC, PT and investigator's verbatim. Additional listings will be provided for serious adverse events (SAEs), TEAEs with grade 3 or grade 4, TEAEs leading to any study drug discontinuation, TEAEs of special interest, and TEAEs with fatal outcome.

In case of rash, all information related to rash assessments will be listed.

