Secondary Endpoints:	
 The proportion of subjects who have a sustained virologic response (SVR; i.e., HCV RNA concentration below the lower limit of quantitation [$<LLOQ$; <15 IU/mL]) at 4, 8, 12, 18 and 24 weeks after the last actual dose of treatment PK parameters for AL-335 (and metabolites), ODV and SMV in plasma The proportion of subjects who experience virologic relapse during the follow-up period. The proportion of subjects who have on treatment failure while receiving study medication Viral kinetics, as determined at different timepoints during treatment by the proportion of subjects who achieve 
 HCV RNA $<LLOQ$ undetectable HCV RNA $<LLOQ$ Time to achieve undetectable HCV RNA and $<LLOQ$ HCV RNA The amino acid sequence of the NS5A, NS5B and NS3/4A proteins at baseline and post-baseline in subjects who fail treatment Effect of various baseline and host disease-related characteristics on treatment outcome
Duration of Treatment and Study Period:	
Up to 43 weeks (from screening through study completion) for each enrolled subject as follows:
 
 Screening: Up to 50 days Study Period: Up to 12 weeks Follow-up: Up to 24 weeks after completion of study medications
Number of Sites and Location:	Up to 50 sites globally
Sample Size:	Up to 320 treatment-naïve and treatment experienced subjects with CHC infection will be enrolled in up to 16 cohorts. Since this is an exploratory study, no formal sample size calculation has been performed. A total sample size of 10-20 subjects/cohort is considered sufficient to explore the safety, pharmacokinetics, and efficacy of the possible study regimens in various HCV-infected subpopulations (e.g., GT1, compensated cirrhosis, etc).

**Inclusion
Criteria:**

Main Inclusion Criteria for All Subjects:

1. Subject has provided written consent.
2. In the Investigator's opinion, the subject is able to understand and comply with protocol requirements, instructions, and protocol-stated restrictions and is likely to complete the study as planned.
3. Male or female, 18–70 years of age.
4. Body mass index (BMI) 18–35 kg/m², inclusive.
5. A woman of childbearing potential must have a negative serum (β -human chorionic gonadotropin) pregnancy test at screening.
6. Female subjects must either:
 - not be of childbearing potential defined as:

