4.5 Subject Completion

A subject will be considered to have completed the study if he or she has completed the assessments at the Week 24 follow-up visit.

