8.1.1 Adverse Events

Adverse events, including pretreatment events, will be recorded from the time of consent through the SVR24 visit. All AEs/SAEs will be coded using the *Medical Dictionary for Regulatory Activities (MedDRA)*.

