### 3.2 Visit Windows and Phase Definitions

Phases will be constructed as follows:

Trial phase	Start date	End date
Screening (phase 0)	Minimum of Date of signing the informed consent and Date of the first screening visit	1 day before the first study drug intake (AL-335+ODV( $\pm$ SMV))
Treatment (phase 1)	Date of first study drug intake (AL-335+ODV( $\pm$ SMV))	Date of last study drug intake: MAXIMUM{Date of last study drug intake (AL-335+ODV( $\pm$ SMV))} + 3 days*
Follow-up (phase 2)	End date of Treatment phase + 1	Trial termination date

\*In case the last study drug intake is missing, other dates can be used instead for date of last study drug intake: E.g. if the subject discontinued treatment (known from the disposition table): date of the withdrawal visit, if the latter is not available: date of first available FU visit minus the number of days in follow-up at which this FU visit was scheduled according to the protocol. If those dates are not available, date of trial termination.

The number of days in the treatment phase (ADY) will be defined as:

$ADY = \text{visit date} - \text{date of first study drug intake} + 1$  for visits on or after the day of first study drug intake

$ADY = \text{visit date} - \text{date of first study drug intake}$  for visits before the day of first study drug intake

In case the date of first study drug intake is missing, the date of the baseline visit can be used as date of first study drug.

Actual End of Treatment visit (EOT) is defined as the last visit in the Treatment phase.

All visits (regardless the investigated parameter) will be allocated within each phase to analysis time points based on the number of days in phase (ADY):

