### 6-Week Cohorts

Trial phase	Target phase day	Analysis time point (numeric version)	Analysis time point b	Time interval (days) a
Screening	$-\infty$	-1	Screening	$<0$
Treatment phase	1	0	Baseline	$\leq 1$
	2	0.2	Day 2	2
	3	0.3	Day 3	[3,5]
	7	1	Week 1	[6,11]
	14	2	Week 2	[12,18]
	21	3	Week 3	[19,25]
	28	4	Week 4	[26,32]
	35	5	Week 5	[33,39]
	42	6	Week 6	[40, $+\infty$ ]
	last visit while on study therapy or 3 days after the day of last dose	999	EOT	
Follow-up phase	25	16	Follow-up Week 4	[1,39]

	53	20	Follow-up Week 8	[40,67]
	81	24	Follow-up Week 12	[68,102]
	123	30	Follow-up Week 18	[103,144]
	165	36	Follow-up Week 24	[145, $+\infty$ ]

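### SAP 8.1 tabulates TEAEs over treatment plus 24 weeks after the last dose with no table by phase, and merges repeat events across both phases

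*SAP*

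**What the plan says.** **Window.** Under SAP 8.1 a TEAE "is an adverse event that occurs after the first IMP administration", or one present earlier that worsens after it. No closing date is given. Events are taken through the completion visits, "for the treatment and follow-up phase combined". Protocol 8.1.1 says adverse events "will be recorded from the time of consent through the SVR24 visit". Protocol 4.5 counts a subject as complete once "he or she has completed the assessments at the Week 24 follow-up visit". The synopsis gives "Follow-up: Up to 24 weeks after completion of study medications". Protocol 7.2.2 refers only to the follow-up visit without naming one, but Table 6-4 schedules AE evaluation at every follow-up visit to Week 24.

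**Phases.** SAP 3.2 defines a Treatment phase (first intake to last intake plus 3 days) and a Follow-up phase that opens at "End date of Treatment phase + 1". No TEAE table in SAP 8.1 or Appendix 3 is split by these phases.

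**Repeats.** If a subject has several events with one preferred term "during the same phase (treatment and follow-up phase combined), only one event is counted". The merged event takes the first start, the last end, the highest intensity and the highest causality. Protocol 7.2.2 says that a recurrence after resolution is reported as a new event with its own grade.

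**Timing shown elsewhere.** SAP 8.1 plans incidence and prevalence per 2-week interval (any AE, and events of special interest), time to first event of interest with Kaplan-Meier curves, bar graphs of worst cardiac grade over time, and listings. Protocol 10.4.1 also asks for by-subject listings by treatment day.

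**The concern.** Safety is the primary endpoint and the synopsis names no comparator. Whether an event arose on drug or after it is therefore one of the few internal contrasts the study offers, and the main TEAE tables do not show it. SAP 8.2 already judges whether a laboratory abnormality is treatment-emergent in a given phase, so the device exists in the plan and is absent only for adverse events.

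Two things are at stake. First, a reader of the SOC/PT, intensity, causality, serious or Grade 3/4 table cannot tell how many events occurred while drug was being taken. Second, the repetition rule changes reported values: event counts, grade, causality, onset and duration can all differ from what the site recorded. Protocol 10.8 plans to pool these data with a Phase 2b study by duration group, so the combined counts would carry into that analysis unless its separate plan says otherwise.

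**Working it through.** **The plan's own safety figure.** Protocol 9.3 gives a 96% chance of seeing an AE of 1% incidence among 320 subjects. 1 − 0.99^320 = 0.960, which agrees. The figures for 0.1%, 0.5% and 0.8% also reproduce (27.4%, 79.9%, 92.4% against 27%, 80%, 92%). Nothing below alters these. The documents state no off-drug share, so it is derived here.

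**Inputs.** Follow-up is 24 weeks (synopsis; protocol 4.5 and 8.1.1). Treatment, w, is 6, 8 or 12 weeks (the three sets of visit windows in SAP 3.2). The SAP's 3-day extension of treatment moves the Week 24 target to day 168 − 3 = 165 of the Follow-up phase.

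**Share of the calendar AE window after the last dose**

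| w (weeks) | 24/(24 + w) | SAP phases: 165/(7w + 3 + 165) |
|---|---|---|
| 6 | 24/30 = 80.0% | 165/210 = 78.6% |
| 8 | 24/32 = 75.0% | 165/224 = 73.7% |
| 12 | 24/36 = 66.7% | 165/252 = 65.5% |

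**Subjects dosed by 6 February 2017.** From protocol Table 1-1, 81 subjects had 8 weeks, 20 had 6 and 22 had 12, which makes 123. On-treatment time is 81×8 + 20×6 + 22×12 = 1,032 subject-weeks. Follow-up, if complete, is 123×24 = 2,952. The share is 2,952/3,984 = 74.1%.

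**The repetition rule, on a hypothetical subject.** Treatment lasts 8 weeks. A Grade 1 event, unlikely related, starts in Week 3 and resolves. The same preferred term returns 20 weeks after the last dose (study Week 8 + 20 = 28) as Grade 3, possibly related.

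- Protocol 7.2.2: two events, each with its own grade.
- SAP 8.1: one event, with on-treatment onset, Grade 3, possibly related, and a span of about 28 − 3 = 25 weeks.
- Rule applied within phase: one Grade 1 event in Treatment and one Grade 3 event in Follow-up.

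The overall number of subjects with a TEAE is one in every case. The event count, the intensity and causality rows, and the apparent timing of the Grade 3 event differ.

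**The case against.** The case for leaving the plan alone has several good parts.

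- **Timing is not lost.** The 2-week summaries, Kaplan-Meier curves, cardiac bar graphs and listings show it, and with 10-20 subjects per cohort a serious or Grade 3/4 event can be placed by hand. This stands, and it limits the point. But the first three cover only any AE or events of interest, and a listing is not a count.
- **Calendar time is not ascertainment.** AE evaluation falls on Days 1, 2 and 3 and weekly on treatment, then at follow-up Weeks 4, 8, 12, 18 and 24. The post-treatment share of contacts is 5/14 = 36%, 5/16 = 31% and 5/20 = 25% for 6, 8 and 12 weeks. A reader might infer that most tabulated events are background. The documents do not support that.
- **Some tables are little affected.** TEAEs leading to drug discontinuation arise while drug is taken. The causality table already sets aside events judged unrelated, although the rule of highest causality still crosses phases there.
- **Late toxicity should be captured.** It should, which is why the combined tables stay.
- **Cohorts are not randomised**, and several differ in genotype, cirrhosis status or regimen. Tables by phase do not make durations comparable, and on-treatment percentages still reflect unequal exposure. That is correct, and no such comparison is claimed.

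**Conclusion.** The point holds as a gap in presentation and a counting rule that needs narrowing. Between 67% and 80% of the calendar AE window (65.5% to 78.6% on the SAP's phases) is post-treatment, no TEAE table separates it, and the repetition rule crosses the boundary. The shares assume that planned treatment and all 24 weeks of follow-up are completed.

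Three stronger readings are not supported:

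- **That a drug effect is diluted.** The tables report the percentage with at least one TEAE, which can only rise as the window lengthens. A risk ratio against background would need assumed hazards; there is no comparator and no planned output computes one. What is weakened is the attribution of events to the on-drug period.
- **That the share applies to all primary safety tables.** Laboratory tests, ECG, echocardiogram, vital signs and physical examination are last scheduled 4 weeks after dosing, so their post-treatment share is 4/(4 + w): 40%, 33% and 25%.
- **That post-treatment means unexposed.** ODV is sampled at follow-up visits to Week 24, and the documents give no ODV half-life. How much of follow-up is drug-free cannot be computed from them.

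**What to change.** In SAP 8.1 and Appendix 3:

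1. Keep the combined TEAE tables.
2. Add TEAE tables by the SAP 3.2 Treatment and Follow-up phases: overall, SOC/PT, intensity, causality, serious, and Grade 3/4. Assign each event by its date of onset (or of worsening), using the date imputation already in SAP 4.
3. Apply the repetition rule within each phase, so that a recurrence in follow-up keeps its own onset, grade and causality.
4. If a longer post-dose window is preferred to last dose plus 3 days, for example to the 4-week safety visit, pre-specify it and say that it is an assumption. Under that choice the later period is 20/(24 + w) of the window: 66.7%, 62.5% and 55.6% for 6, 8 and 12 weeks.

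The cost is SAP wording and repeat runs of existing tables, with more output to review and one cut-off to agree. No new data, visits or subjects are required.

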7.2.2 Documenting and Reporting AEs

Record all AEs that occur from Day 1 (from start of study medication administration) to the follow-up visit, regardless of the intensity, seriousness, or relationship to study drug, on the AE CRF, for all enrolled subject. Subjects who do not enroll (i.e., screen failures), collect AEs until the time of screen failure.

Once an event has resolved, any recurrence will be reported as a new event with a corresponding grade.

Clinically significant changes in objective findings (e.g., laboratory, ECG, physical examination) should be considered AEs only if they meet the following criteria:

- Associated with accompanying symptoms; and/or,
- Require medical/surgical intervention; and/or,
- Lead to discontinuation from the study; and/or
- Lead to significant additional concomitant drug treatment, or other therapy; and/or,
- Lead to any of the outcomes included in the definition of an SAE.

Whenever possible, the etiology of the abnormal findings (rather than the abnormal finding(s) itself) should be documented as the AE. Repeated additional tests and/or other evaluations required to establish the significance and etiology of an abnormal result should be obtained when clinically indicated. An AE includes the following:

- Pre-existing event that increases in frequency or intensity.
- Condition detected or diagnosed during the study period, even though it may have been present, in retrospect, prior to the first dose of study drug.
- Laboratory abnormalities outside of normal limits and requiring therapeutic intervention.
- An overdose of the study drug without any signs or symptoms will be considered an AE. A calculated dose that exceeds its correct dose by 10% or more and is administered to the subject will be considered an overdose and documented as an AE.

The following events **will not** be identified as AEs in this study:

- Progression or exacerbation of the subject's underlying disease. However, clinical sequelae that result from disease progression, such as pleural effusion or small bowel obstruction, are reportable as AEs.
- Medical or surgical procedures (e.g., surgery, endoscopy, tooth extraction, etc); however, the condition (the "triggering event") that leads to the procedure may be an AE.
- Pre-existing conditions present or detected prior to the first dose of study drug that do not worsen.

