9.2 Study Endpoints

9.2.1 Primary Endpoint

- Safety data including but not limited to tabulation of AEs, physical exam, vital signs, 12-lead ECGs, echocardiogram, and clinical laboratory results (including chemistry, hematology, and urine).

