**12-Week Cohorts**

Trial phase	Target phase day	Analysis time point (numeric version)	Analysis time point b	Time interval (days) a
Screening	-∞	-1	Screening	<0
Treatment phase	1	0	Baseline	≤1
	2	0.2	Day 2	2
	3	0.3	Day 3	[3,5]
	7	1	Week 1	[6,11]
	14	2	Week 2	[12,18]
	21	3	Week 3	[19,25]
	28	4	Week 4	[26,32]
	35	5	Week 5	[33,39]
	42	6	Week 6	[40,46]
	49	7	Week 7	[47,53]
	56	8	Week 8	[54,60]
	84	12	Week 12	[82, +∞]
		last visit while on study therapy or 3 days after the day of last dose	999	EOT
Follow-up phase	25	16	Follow-up Week 4	[1,39]
	53	20	Follow-up Week 8	[40,67]

	81	24	Follow-up Week 12	[68,102]
	123	30	Follow-up Week 18	[103,144]
	165	36	Follow-up Week 24	[145, +∞]

a The reference day of the Treatment and Screening phase is the day of the first study drug intake (= day 1 in Treatment phase).

b Target day in follow-up phase equals target day in the protocol minus 3 days.

If two visits fall within the same interval, the last measurement within the interval will be used for the descriptive statistics/tabulations per time point and graphics in order to have only one evaluation per subject per analysis time point. If there are two measurements on the same day and time, then the measurement with the highest sequence number will be used. Listings will include all values.

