#### **Handling of missing and retest values**

No management of missing data will be done, except for pharmacokinetic values (see [section 7.1](#)) and missing or incomplete start/stop dates (see below).

Missing start or end dates for events not aligned to a specific visit/week such as adverse events, medications reported, etc., will be imputed using the following rules:

- A completely missing start date of an event will be set to the date of the first dose of study medication, unless it is clearly indicated that this is an event happening pretreatment. In this case, it will be set to the day before the first dose of study medication.
- A completely missing stop date will not be imputed, but the event will be assumed to be ongoing.
- Partially missing dates where the year is known will be set to 01 January of that year or the first dose of study medication date, if the first dose of study medication occurred in that year.
- Partially missing dates where the year and month are known will be set to the first day of that month or the first dose of study medication date, if the first dose of study medication occurred in that month.

If, by applying the above rules, the stop date is imputed before the start date, then the stop date will be set to be the same as the start date.

For all parameters and for subjects with retest values, the last reliable value will be used as a measurement time before the first investigational medicinal product (IMP) administration (provided it was measured before IMP administration) and the first reliable value will be used as a measurement time after the first IMP administration.

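### Three SAP data-handling rules distort or leave contradictory the by-time safety outputs: merging of repeat AE episodes, imputation of partial stop dates, and choice of retest value

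*SAP*

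**What the plan says.** Protocol 9.2.1 makes safety the primary endpoint: "Safety data including but not limited to tabulation of AEs, physical exam, vital signs, 12-lead ECGs, echocardiogram, and clinical laboratory results". The analysis is descriptive.

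- **Repeat episodes (SAP 8.1).** If a preferred term recurs in a subject "during the same phase (treatment and follow-up phase combined), only one event is counted". Its start is that of the first occurrence, "the end time will be the end time of the last episode", and intensity and causality are the highest recorded. The same section plans: "The incidence and comparable prevalence rate per 2-week time interval for any AEs will be summarized and plotted by cohort". It plans the same for AEs of special interest, and bar graphs of worst cardiac grade over time. Protocol 7.2.2 collects recurrences separately: "Once an event has resolved, any recurrence will be reported as a new event with a corresponding grade".
- **Partial dates (SAP 4).** One rule covers start and end dates: "Partially missing dates where the year and month are known will be set to the first day of that month", or to the first-dose date if that lies in the same month. With only the year known, the date becomes 1 January, or the first-dose date if that lies in the same year. A stop date that then precedes the start is raised to the start. A completely missing stop date means ongoing.
- **Retests.** SAP 4 says, for all parameters, that "the first reliable value will be used as a measurement time after the first IMP administration". SAP 3.2 says that when two visits share a window "the last measurement within the interval will be used for the descriptive statistics/tabulations per time point and graphics", with the highest sequence number deciding between records at the same day and time. Neither section says which prevails.

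**The concern.** The trial is open-label with no comparator. When an event starts, stops and worsens relative to dosing is therefore a large part of the evidence on drug effect, and the two-week and by-visit outputs exist to show it.

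Merging makes events look longer and removes later onsets from interval incidence. The stop-date rule makes on-study events look shorter. The two act in opposite directions on prevalence, so even the sign of the net error is unknown. The retest sentences allow two different by-visit tables from the same data.

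Cardiac events matter most here. Protocol 1.3 names the heart as a target organ of ODV toxicity, and Protocol 1.2.1.2 mentions a case of progressive PR prolongation with Wenckebach phenomenon in this study. If the cardiac graph used merged records, a later, worse episode under the same term would be shown from the first, milder onset.

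**Working it through.** The plan states no figure on this point. Its only numerical safety statement (Protocol 9.3) reproduces: 1 − 0.99^320 = 96.0%. It is not affected.

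**1. Merging.** Assumption: two-week intervals are 14-day blocks from Day 1 (the SAP gives no origin). Day d lies in block floor((d − 1)/14) + 1. Kept as episodes, an AE occupies only the blocks it touches. Merged, it occupies every block from first start to last end.

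| Assumed episodes | Blocks, by episode | Blocks, merged | Days, by episode | Days, merged |
|---|---|---|---|---|
| Days 3–4 and 33–34 | 2 | 3 | 4 | 32 |
| Days 3–4 and 63–64 | 2 | 5 | 4 | 62 |
| Days 3–4 and 80–81 | 2 | 6 | 4 | 79 |
| Day 3 and Day 160 | 2 | 12 | 2 | 158 |

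For the last row, floor(159/14) + 1 = 12 and 160 − 3 + 1 = 158. In each row the number of onsets falls from 2 to 1. The column giving the number of TEAEs also loses recurrences. Protocol 1.2.1.1 reports, from another study, two toothache events in one subject; this rule would count one.

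**2. Partial stop dates.** Assume the first dose was in April.

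- True dates 20 May to 9 June, stop recorded as June. The true duration is 12 + 9 = 21 days. The imputed stop is 1 June, giving 12 + 1 = 13 days.
- True dates 5 to 18 June, stop recorded as June. The true duration is 14 days. The imputed stop of 1 June is raised to 5 June, giving 1 day.

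Before the floor at the start date, backdating is 0 to 30 days, with mean 15 in a 31-day month. The floor reduces it. A simulation with first dose on a random calendar day, onset uniform over Days 1–56 and month-only stop dates gave:

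| True duration (days) | Mean imputed duration | Reduced to one day | Mean blocks, true | Mean blocks, imputed |
|---|---|---|---|---|
| 3 | 1.1 | 93% | 1.14 | 1.01 |
| 7 | 1.7 | 80% | 1.43 | 1.05 |
| 14 | 4.0 | 58% | 1.93 | 1.21 |
| 28 | 13.4 | 11% | 2.93 | 1.88 |

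A year-only stop in the first-dose year goes to the first-dose date and is then raised to onset. Every AE that starts on treatment or later that year becomes a one-day event. With no stop information at all, the same AE is ongoing.

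**3. Retests.** The Week 4 window is Days 26–32 (SAP 3.2), and Protocol 7.5.1 repeats CK about every 72 hours once it is at least 3×ULN. With assumed values:

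| Measurements in one window | First value (SAP 4) | Last value (SAP 3.2) |
|---|---|---|
| CK 12×ULN on Day 28, 2×ULN on Day 31 | DAIDS Grade 3 | below Grade 1 |
| ALT 12×ULN, then confirmatory 4×ULN | DAIDS Grade 4 | DAIDS Grade 2 |

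Other protocol-triggered repeats are for PR above 240 msec (7.5.2) and for Grade 4 ALT/AST above twice baseline or Grade 4 bilirubin (7.9).

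**The case against.** The strongest reply is that little of the primary endpoint depends on these rules. That is largely right. Subject counts by term, grade and causality do not change with merging. Time to first occurrence needs only the first onset, although an imputed start date can move it. Worst-value laboratory, vital-sign and ECG tables use all scheduled and unscheduled values, and listings show everything. A reader might infer that the primary endpoint as a whole is distorted; the documents do not support that.

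Further points, and what stands of each:

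- *The merging note is only a counting rule, and Protocol 7.2.2 governs recording.* The protocol and SAP do not strictly contradict each other here. But subject counts need no end time, whereas interval prevalence does, and no output is exempted. That the cardiac graph uses merged records is an inference: the SAP neither says so nor rules it out.
- *The stop-date effect is easily overstated.* It is tempting to say that imputation always gives the shortest duration, or that a year-only date can lose up to a year. The first fails for an event begun before dosing, where the first-dose clause can lengthen it. The second exceeds the 12 + 24 weeks of treatment and follow-up. The SAP's output list has no AE duration table, so the effect falls mainly on two-week prevalence, and short events often stay within one block.
- *The retest sentences can be reconciled: SAP 4 within a visit, SAP 3.2 between visits.* The SAP does not say so. An unscheduled CK repeat three days later is both a retest and a second visit, so both sentences apply, and the sequence-number rule still favours the later record.
- *Repeats are limited.* A reader might infer that the protocol mandates them after any abnormal value. It sets thresholds, and the repeat echocardiogram after an EF decline is optional. Some repeats will fall in another window or be run only locally, while central results feed the database (Protocol 8.1.2).

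**Conclusion.** The point holds for outputs over time. Read literally, SAP 8.1 counts event-free gaps as AE time in two-week prevalence, removes later onsets from interval incidence and undercounts events. SAP 4 shortens on-study AEs with partial stop dates: by at most 30 days for month-only dates and less after the floor, and to one day for year-only stops in the first-dose year. It treats AEs with no stop date as ongoing, so partial knowledge tends to give the shortest event and none the longest. SAP 3.2 and SAP 4 conflict over post-baseline retests, which affects by-visit laboratory, vital-sign and ECG summaries.

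The real size cannot be computed, because the documents give no frequency of recurrences, partial dates or retests; every example rests on assumed dates and values. No hypothesis test is planned, so no error rate or power is involved. The change should be made before database lock.

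**What to change.** 1. **SAP 8.1.** Limit the collapsing of episodes to subject counts. Use individual episode dates and grades for event counts, two-week incidence and prevalence, and grade-over-time plots, and state this for the cardiac graph.
2. **SAP 4, dates.** Give stop dates their own rule: last day of the known month or year, capped at trial termination. This can overstate duration (the 5 to 18 June example becomes 26 days instead of 14), but that error is conservative for safety.
3. **SAP 3.2 and 4, retests.** Keep one post-baseline rule: the scheduled value for by-visit means, and the worst value in the window for by-visit abnormality counts. Delete the conflicting sentence. SVR keeps its own algorithm in SAP 9.2.1.

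The cost is SAP wording and small programming changes. No new data are needed, since the protocol already has each recurrence recorded as its own event.
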